All items from step 2 (Eligibility Screening), plus below items:

RAs conduct final exit interview

Study nurses conduct study exit plans / transfer of care

Step 6: Post-Study Follow-up Visits (every 6 months for 12 months after Final Assessment - Participants in all study arms)

RAs conduct follow-up interviews and perform pill counts.

Study nurses collect blood samples and vital signs; track visits (dates, clinician type), diagnoses, prescription drugs (names, doses, pill counts of cardiovascular drugs), and medical events

Study nurses record and reconcile medication lists at every visit, and note changes in medications.

The 12-month post follow-up visit will follow the same protocol as Step 5.

III. Subject Selection

Eligibility: Eligible subjects will have incident or prevalent (i.e., first episode or chronic) cases of SMI. In this study we have defined SMI as schizophrenia, schizoaffective disorder, or bipolar disorder. The study's definition of SMI also includes subjects with major depressive disorder, or psychosis NOS with some evidence of functional impairment (an inability to work or live independently and/or being on disability income). Note that the bipolar patients, and some unipolar depression patients, at our study site generally have severe disease and many are on chronic 2GA regimens. Also, many subjects with MDD at our study sites have psychotic features and require chronic 2GA treatment as well. Subjects must have received standing treatment with a 2GA anytime in the past 6 months, and receive their mental health care at one of 4 study sites: McLean Hospital, BayCove Gill Clinic, Mass Mental Health Center, Edinburg Center or Massachusetts General Hospital Outpatient Bipolar Clinic. We will not carry out diagnostic interviews and instead will include all patients with an eligible chart diagnosis, as indicated by subject's psychiatrist, in order to maximize the representative nature of the sample and to more closely approximate how this intervention could be operationalized in real-world practices.

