- Incident or prevalent cases of SMI: including schizophrenia, schizoaffective disorder, bipolar disorder, major depressive disorder, and psychosis NOS with some evidence of functional impairment.
- Age 18 years and older.
- Recent treatment with a 2GA, e.g., having received treatment with a standing 2GA anytime in the past 6 months. Concomitant psychotropic medications will be allowed as there are no contraindications with this regimen. Ongoing treatment of their mental illnesses at one of three mental health clinics: McLean Hospital (McLean outpatient clinicians), BayCove, Edinburg Center, and Mass Mental Health Center, defined as entering one of the treatment programs as a de novo patient (new disease) or having been diagnosed >2 years ago and had at least six visits in the past 12 months (prevalent disease).

The exclusion criteria are as follows:

Unstable/active disease or potential contraindications, e.g., diabetes, unstable
angina or recent acute coronary syndrome, pregnancy, very high risk factors on
the screening labs (e.g., CPK>2*ULN, liver disease (AST> 2*ULN ALT> 2*ULN)

; A1c>7%;), renal failure (creatinine ≥1.3mg/dL or GFR<60 mL/min/1.73m²), liver failure, or both statin and angiotension drug contraindications (when possible we will provide the study medication that does not interact with previously prescribed medications, i.e. subjects taking lithium will only be prescribed simvastatin since anti-hypertensives are contraindicated with lithium). Participants whose screening labs indicate high cholesterol (LDL > 200 mg/dL), hypertension (SPB > 160 mmHg), or hypotension (SBP< 120 mmHg) will be included; however we will not prescribe both study medications; we will only provide the study medication that can be taken safely. For example, a participant with high cholesterol will be referred to their PCP for care and administration of a statin, but could still receive losartan in the treatment arm.

- Unable to provide informed consent, e.g., has dementia, developmental disability, other cognitive disorder, or fails screening mini-mental status exam.
- Women who are pregnant or breastfeeding

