Outpatient Bipolar Clinic. After running data queries using the study's inclusion and exclusion criteria, we will request detailed data through RPDR in order to directly contact those patients who are eligible for the study and who have consented to be contacted in future for research purposes. Detailed data requests, including identifying information such as medical information and contact information, will be approved by the Partners IRB.

Random (1:1) allocation: We will assess eligibility, NP's will conduct the informed consent process, then randomize eligible subjects to one of two arms: 1) fixed-dose statin and/or ARB; or 2) usual treatment with greater monitoring. In both arms, the patient's clinical care remains within the original mental health clinics. We will use a computerized random number generator. Participants unable to be randomized due to eligibility issues discovered at the first study visit will still be followed as not-randomized subjects.

Randomization scheme: We will start with a concealed, simple subject-level randomization scheme, e.g., web or telephone delivered random sequence. [104-106] We also will consider concealed, block randomization schemes, e.g., accounting for clinic and time with randomly varied block sizes. An investigator not involved in the arm assignment or clinical care of subjects will perform the generation and allocation concealment.

Intervention: The multi-component intervention exploits a number of strategies from incentive theory and behavioral economics, including: a) a simplified drug regimen; b) free treatments; c); framing of goals and goal setting; and d) focus on immediate cardiovascular risks within a larger plan for risk reduction.^[107-114]

Control: We will compare the initial treatment intervention with usual treatment (control arm), with both arms superimposed on a system of regular monitoring base. The RA/APRN pair will make no effort to alter or influence treatment or use of that treatment for subjects in the control arm. Note that our goal in the Control arm is to characterize "usual treatment". We will not intervene in this care except in emergencies requiring us to notify the patient's treatment team. Some patients who need care for metabolic syndrome may not be receiving it – just as they would if not in our trial.

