In order to receive a bonus, Follow-Up #2 and Follow-Up #3 need to be scheduled and attended within one month after the end of the scheduling window in order to receive the bonus. If the participant completes the visit outside of the scheduling window, they will still get paid the baseline payment of \$20.00. The scheduling window refers to the two-week window within which a visit is due, which is 83 days from the prior visit. A member of the study team will contact participants to let them know when visits are due.

- If a participant completes Follow-Up #1, then staff will compensate \$40.00 for Follow-Up #2.
- If a participant completes Follow-Up #1 and Follow-Up #2, then staff will compensate \$60.00 for Follow-Up #3.
- If a participant completes Follow-Up #1 or Follow-Up #2 (but not both visits), then compensation for Follow-Up #3 will be \$40.00

V. Study Procedures

Study Site: The study will take place at four sites: McLean Hospital, BayCove Gill Clinic, Mass Mental Health Center, Edinburg Center, and Massachusetts General Hospital Outpatient Bipolar Clinic. Study procedures will be the same at each site. Study staff will bring all study equipment, including study drugs, with them to the separate sites and carry out all study procedures, leaving no burden on staff from these sites.

Contacting patient's current treater: The only information to be shared with the PCP is the "PCP letter" (included in the IRB application). This letter will be sent out between the inclusion/exclusion visit, only for patients eligible to be randomized, and the randomization visit, when we find out what arm of the study the patient is going into. Since this letter is sent prior to randomization, the letter does not include information on what study arm the patient is assigned to. The letter states that the participant will be explicitly removed from the study if requested by the PCP for medical purposes. The logic of this design is as follows: ours is a randomized open-label study. The treatment as usual arm is intended to capture naturalistic primary care of our patients while the intervention arm tests the impact of a cardiovascular preventive regimen. In these trials, "contamination" across study arms is a major concern. This refers to a process

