Characterization of Usual Treatment: We also will carefully describe care under Usual Treatment, including the timing of initiation, treatment choice, adherence, prescribing clinicians, and visit patterns for subjects in the control arm. We will characterize the involvement of other clinicians for subjects in both arms, and clinic traits.

Treatment Operational Definition: To start, we will use the same treatment definition for both study arms, i.e., current use of a statin and angiotensin drug. Because there are multiple potential drugs for cardiovascular prevention, we will alter this definition in a series of sensitivity analyses. For example, we will examine a minimal cardiovascular treatment variable in which we define treatment as current use of any cardiovascular drug, independent of the therapeutic class or mechanism of action. We also will examine a partial treatment variable in which we count the number of distinct cardiovascular prevention drugs.

Analysis approach 1: We will plot the percent on "adequate" CVD prevention care, at baseline and the four quarterly follow up times to monitor how treatment activity unfolds over time in the two arms of the trial. At any given follow-up point we will be comparing

two binary outcomes (on or off treatment) and will use standard methods for comparing two proportions to test statistical significance and get confidence intervals for the difference in the percent on treatment in the two arms. We will use a Bonferroni correction so the four separate tests or CIs will have an overall level of 0.05 or 95% CI, respectively.

Analysis approach 2: We will use all available follow-up data to construct a summary measure of the mean percentage of follow-up time during which each group was on treatment. Since we expect the distribution of outcomes to be non-normally distributed, we will get a test of significance for no difference between the mean outcomes in the two arms using a randomization test. A 95% confidence interval for the difference of percentage of time on Tx will be obtained using bootstrap methods. We will use STATA 13.0 for all analyses.

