Primary study outcome: The main outcome is use of the cardiovascular prevention medications over the 12-months after study initiation. For each individual, we define the primary outcome as the proportion of the 12 follow-up months during which she/he either received any of the prescribed medication or the medication became clinically contraindicated after trial entry (as decided by the treating physician). We will assess the outcome using medication counts at each study visit (i.e., at the 3-, 6-, 9-, and 12-month study visit), supplemented by subject self-reports and the clinic chart review. For subjects who are eligible to receive both statins and ARB medications at baseline, we will calculate the number of days that they receive both medications during the 12 months of follow-up. For subjects who are eligible to receive only one of the two medications at baseline (i.e., because of pre-existing therapy with or because of contraindications to the other prevention medication before trial entry), we will calculate the number of days that they receive the medication during the 12 months of follow-up, with the same approach for addressing changes in subsequent eligibility.

Analysis of the primary study outcome: The primary analysis will follow the intention-to-treat (ITT) principle. We will use regression analysis to estimate the mean average of the primary outcome in each group and the difference between the mean outcomes, along with its 95% confidence interval and using the p-value for a null hypothesis. If clinically meaningful imbalances are detected in baseline covariates despite randomization, we will adjust for those covariates. If necessary, we will adjust for selection bias due to loss to follow-up via inverse-probability weighting. In supplemental analyses to the main ITT approach, we also will conduct appropriately adjusted per-protocol analyses. We will use STATA 13.0 for all analyses. We also will examine a number of pre-specified subgroup analyses, in which we examine whether the intervention might be more effective among those SMI patients who are more likely to receive fragmented care or less likely to be adherent to complex treatment regimens, e.g., SMI patients with Medicaid versus those with commercial health insurance.

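### The allocation scheme is left open and no analysis of medication use prespecifies clinic or block: some precision is lost and, if clinic blocks were used, the intervals are slightly too wide

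*Protocol*

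**What the plan says.** **Allocation.** Protocol, IV. Subject Enrollment, sets the ratio under "Random (1:1) allocation". Under Randomization scheme it says "We will start with a concealed, simple subject-level randomization scheme", and then: "We also will consider concealed, block randomization schemes, e.g., accounting for clinic and time with randomly varied block sizes". It gives no trigger or date for a change. The SAP does not mention allocation.

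**Analyses of use.** Protocol, VI. Biostatistical Analysis, Aim 1, has two approaches. Approach 1 compares the arms' proportions on treatment at each of four follow-up visits by standard two-sample methods. Approach 2 takes the mean percentage of follow-up time on treatment: "we will get a test of significance for no difference between the mean outcomes in the two arms using a randomization test", with a bootstrap interval. Neither approach names clinic, period or block. The SAP (Analysis of the primary study outcome) says: "We will use regression analysis to estimate the mean average of the primary outcome in each group and the difference between the mean outcomes". It then allows adjustment for baseline covariates if imbalances judged to matter clinically are found. It lists no covariates and sets no threshold.

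**Clinics.** The counts disagree. Protocol, III. Subject Selection, has "one of 4 study sites: McLean Hospital, BayCove Gill Clinic, Mass Mental Health Center, Edinburg Center or Massachusetts General Hospital Outpatient Bipolar Clinic", which says four and names five. V. Study Procedures has "The study will take place at four sites" and again names five. The inclusion criterion has "Ongoing treatment of their mental illnesses at one of three mental health clinics" and names four.

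**The concern.** Clinic may well predict use. Control-arm use arises from usual care (VI, Analysis of Aim 1). One named site is a bipolar clinic, lithium users can be given only one of the two study drugs, and the SAP counts the outcome differently for one-drug and two-drug subjects. The Protocol itself offers clinic as a blocking factor. None of this gives the size of a clinic effect.

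If clinic is prognostic, an analysis without it leaves clinic variation in the error term. If allocation was also blocked by clinic, the standard error ignores a restriction that the design imposed. The SAP's rule then works the wrong way round. Clinic enters only when it is imbalanced, but blocking keeps it balanced, so the rule stays silent in the one case where clinic is needed for a correct standard error. What is at stake is precision on the primary question, and whether the choice to adjust is fixed before the data are seen.

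**Working it through.** **Inputs.** From the Protocol (Power Calculations): 150 per arm, control use below 15% (15% used here), a 20-point difference, and one-sided alpha 0.0125. Assumed, because the documents give nothing: five clinics of 60, and a clinic share R² of outcome variance of 2% to 10%. The plan has no figure of its own for clinic, so there is none to reproduce. Its power statement makes no allowance for clinic and is a separate matter.

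**1. Chance imbalance under simple allocation.** For one clinic of 60, a split of 36:24 or worse has probability 2 × P(Bin(60, 0.5) ≥ 36) = 2 × 0.0775 = 0.155. For at least one of five it is 1 − (1 − 0.155)^5 = 0.57. Imbalance is therefore likely, but its effect is small. With arms of 150, a 36:24 clinic makes up 36/150 = 24% of one arm and 24/150 = 16% of the other. If use there differs from the other clinics by an assumed 10 points, the contrast moves by 0.08 × 10 = 0.8 points.

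**2. Validity under simple allocation.** In a simulation (300 subjects, five clinics of 60, outcome SD 0.4, 6,000 runs per setting, R² from 0 to 0.20), the unadjusted standard error was 1.00 to 1.02 times the empirical SD. Type I error was 4.4% to 4.9%. The only loss is precision. Adjustment would cut the variance by roughly R², the equivalent of 300 × 0.02 = 6 to 300 × 0.10 = 30 subjects.

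**3. Clinic blocks used but ignored.** The ratio of reported to true standard error is f = 1/√(1 − R²). The true two-sided error of a nominal 5% test is 2 × P(Z > 1.96 f). The last two columns are simulated under clinic blocks of 2, 4 and 6.

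| R² | f | Error by formula | Simulated, no clinic term | Simulated, clinic term |
|---|---|---|---|---|
| 0.02 | 1.010 | 4.8% | 4.5% | 4.7% |
| 0.05 | 1.026 | 4.4% | 4.5% | 4.8% |
| 0.10 | 1.054 | 3.9% | 3.4% | 4.3% |

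At R² = 0.20, beyond the range taken as plausible, f = 1.118.

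**4. Power for a continuous outcome.** For an assumed effect of 0.13 with SD 0.4 under blocks, the clinic term raises power from 80.8% to 82.3% (R² = 0.05) and from 82.5% to 85.1% (R² = 0.10).

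**5. Binary check at one visit.** Assume clinic control rates of 5%, 10%, 15%, 20% and 25%, each 20 points higher in the intervention arm.
- Unadjusted SE = √[(0.15 × 0.85 + 0.35 × 0.65)/150] = √(0.355/150) = 0.0486.
- Stratified SE uses the mean within-clinic variances: √[(0.1225 + 0.2225)/150] = √(0.345/150) = 0.0480.
- Ratio 1.014, so 1.4% too wide. Under blocks, power at one-sided 0.0125 is 97.1% unadjusted and 97.3% stratified.

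**The case against.** The strongest reply is that simple allocation is the only scheme the Protocol commits to, and under it nothing is invalid. The unadjusted estimate is unbiased, its interval already covers chance imbalance, and simple allocation is the least predictable scheme, which has value in an open-label trial. All of this stands. The 57% in step 1 measures how likely an uneven split is; it does not measure harm.

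Second, the SAP has a route by which clinic could enter. A reader might infer that any clinic imbalance is simply left in; that clause does not support the inference. What remains is that the clause depends on the observed data, names no covariate, sets no threshold, covers only the SAP regression, and would not act under blocking.

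Third, the blocks are only a possibility. A reader might also infer that the randomization test will permute freely across clinics. The Protocol does not say so: such a test can follow the actual allocation, and the text is silent on whether it will.

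Fourth, the clinic effect is not sourced. Primary care physicians practise elsewhere, and the same study procedures are used at every site. That is a fair reason to expect a modest R², and the result is shown as a range for that reason.

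**Conclusion.** The point holds as a small, nearly free improvement. It does not show an invalid analysis. Under simple allocation, only precision is lost. If clinic blocks were used, unadjusted intervals are about 1% to 5% too wide for an assumed R² of 2% to 10%, and two-sided type I error falls somewhat below 5%. The error is conservative throughout; nothing here inflates false positives. The figures rest on five equal clinics and the assumed R².

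Two further inferences are not supported. One is that Aim 2 escapes because its subject fixed effects absorb clinic. They remove only constant differences in level, while Aim 2 contrasts profiles of change, so clinic differences in change remain. The other is that the remedy is to block from the first participant. The Protocol's Trial Study Design Overview reports that some people randomized to the intervention have already stopped study medication, so allocation has begun and the remedy has to lie in the analysis.

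**What to change.** In the SAP, before outcome data are examined:

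- State which allocation scheme was used and the date of any switch.
- Include clinic indicators in the primary regression regardless of observed imbalance, and period indicators as well if allocation was blocked by time.
- At the four visits, report a clinic-stratified (Mantel-Haenszel) risk difference.
- Run the randomization test and the bootstrap according to the scheme actually used, within clinic and period strata wherever allocation was blocked.
- Reconcile the clinic count across III. Subject Selection, the inclusion criterion and V. Study Procedures, so that the strata are defined.

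Clinic terms are valid under simple allocation too, so the change does not depend on which scheme was used. The cost is some wording and, with five clinics, four degrees of freedom out of 300 subjects, plus a few more if period is needed.

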In order to receive a bonus, Follow-Up #2 and Follow-Up #3 need to be scheduled and attended within one month after the end of the scheduling window in order to receive the bonus. If the participant completes the visit outside of the scheduling window, they will still get paid the baseline payment of \$20.00. The scheduling window refers to the two-week window within which a visit is due, which is 83 days from the prior visit. A member of the study team will contact participants to let them know when visits are due.

- If a participant completes Follow-Up #1, then staff will compensate \$40.00 for Follow-Up #2.
- If a participant completes Follow-Up #1 and Follow-Up #2, then staff will compensate \$60.00 for Follow-Up #3.
- If a participant completes Follow-Up #1 or Follow-Up #2 (but not both visits), then compensation for Follow-Up #3 will be \$40.00

V. Study Procedures

Study Site: The study will take place at four sites: McLean Hospital, BayCove Gill Clinic, Mass Mental Health Center, Edinburg Center, and Massachusetts General Hospital Outpatient Bipolar Clinic. Study procedures will be the same at each site. Study staff will bring all study equipment, including study drugs, with them to the separate sites and carry out all study procedures, leaving no burden on staff from these sites.

Contacting patient's current treater: The only information to be shared with the PCP is the "PCP letter" (included in the IRB application). This letter will be sent out between the inclusion/exclusion visit, only for patients eligible to be randomized, and the randomization visit, when we find out what arm of the study the patient is going into. Since this letter is sent prior to randomization, the letter does not include information on what study arm the patient is assigned to. The letter states that the participant will be explicitly removed from the study if requested by the PCP for medical purposes. The logic of this design is as follows: ours is a randomized open-label study. The treatment as usual arm is intended to capture naturalistic primary care of our patients while the intervention arm tests the impact of a cardiovascular preventive regimen. In these trials, "contamination" across study arms is a major concern. This refers to a process

whereby the usual clinical care is enhanced due to awareness of the study aims. Clinicians who are aware that their patients' care is being evaluated on certain criteria may consciously or unconsciously pay more attention to these criteria. This effect typically makes the treatment as usual arm appear more robust and reduces the odds of detecting an intervention effect. Our goal is to avoid this contamination effect while also ensuring that PCPs are adequately informed and have an opportunity to intervene if they deem it necessary. As per our study design, there is no ongoing communication with the PCP. By sending them a letter before study arm assignment, we ensure that the PCP can request the patient be excluded. As the individual responsible for the overall medical care of the participant, the PCP has the power to veto patient participation in this study. The PI's name and contact information on this study will be included in the PCP letter so that the PCP may contact the PI with study design questions. If the PCP desires to know whether the patient is going on the medication arm they then have to go through routine channels (e.g. ask the patient) to obtain this information. If the PCP contacts the research team asking for this information, we will provide it. But this approach minimizes "contamination" from the study team, and approximates routine clinical care if the patient were placed on a medication by another clinician. To further minimize contamination we will not communicate routine lab results to the PCP. However if in the course of the study, should lab results require immediate attention, study nurses will triage and contact subject PCP accordingly.

We will send another letter at study completion informing the participant's PCP of the treatment the participant received as a part of their study.

Anytime staff attempts to contact a participant's PCP or any other provider, staff will confirm the contact information with the participant prior to attempting communication. This will be done to ensure that the participant still receives care from the indicated provider, as participants occasionally change clinics over the course of the study period.

Data Collection: During Recruitment (Step 1 in T1), all participants, or their legal surrogates, will complete a Consent Survey that asks 11 simple questions about the study such as "What is being studied in this study?" and "Will you lose any of your services or benefits if you refuse to participate?" For participants, or guardians/healthcare proxies who do not answer correctly, the study nurse or RA will repeat the information and re-administer the survey. Participants who still cannot complete the survey correctly will be excluded. Participants, or their guardians/proxies, do not need to answer each question exactly as indicated, but rather demonstrate understanding of the correct answer (e.g. participant does not need to provide the names of every illness studied in the research project, but can simply name one or say "psychotic disorders"). The participant's legal surrogate or proxy will make decisions using "substituted judgment," meaning that the surrogate must consider the subject's own views when consenting to this study. The relationship between the guardian or proxy and participant will be recorded on the informed consent form. Participants with legal guardians must still assent to the study verbally and through signing the consent form. Participant assent will be gauged at every study visit, informed consent being

acquired if and when a participant regains legal power of consent. The study visits will consist of 30-minute interviews with the study nurse, followed by 30-60 minute interviews with the RA. The study nurse will collect vital signs, blood samples, and prescribe the fixed-dose study medications for the intervention group. The nurse will also collect information on side effects/adverse events on medication, medication changes, information on ED visits/hospitalizations/PCP or other clinician visits/any other service utilization for medical/psychiatric purposes. The medication adherence assessment will include: self-report, RA pill counts, review of medical records, and independently collected pharmacy data (e.g., APCD) to examine drug dispensing. We will calculate chlorpromazine (CPZ) equivalents for standardized 2GA dose estimates. In the RA portion of the visit, we will collect ancillary clinical data using standardized forms. Examples of potential items include age, gender, living condition, employment status, internet access, cancer screening history, socioeconomic status (using the Hollingshead scale), social support (using the Duke social support and stress scale), food and diet questionnaires, non-cardiovascular medical conditions, cardiovascular disease risk (using the Global CVD risk assessment), estimated IQ (using the North American Adult Reading Test), smoking status (using the Elyse Tobacco Questionnaire and the Fagerstrom Test for Nicotine Dependence), and clinical insight (using the Scale for Unawareness of Mental Disorder, SUMD). RAs will assess cognition using the BACS (Brief assessment of cognition in schizophrenia). In addition, the RA will complete the WHODAS 2.0 (WHO Disability Assessment Schedule) which assesses cognition, mobility, self-care, social interactions, and life activities (work, school etc.).[116-119] Subjects will also be assessed on their medication attitude and adherence (using the Drug Attitude Inventory, the Voils medication adherence scale, and the Physician Trust Scale). We will refine the standardized data collection; assess feasibility, interpretability, and respondent burden; insure that the final instruments are feasible within the 30minute interview; and insure that our instruments are consistent with current literature and latest expert opinion.

At baseline and all subsequent visits, the RAs will quantify psychiatric symptoms; we will train and periodically test RAs ability to do this. Since the SMI participants will be mixed diagnostically, the RA will complete symptom assessments; examples include the Positive and Negative Syndrome Scale (PANSS), Scale for Assessment of Positive Symptoms (SAPS), and Scale for Assessment of Negative Symptoms (SANS) for psychosis but also the Montgomery-Asberg Depression Rating Scale (MADRS)^[120] Young Mania Rating Scale (YMRS),^[121] Multnomah Community Assessment Scale (MCAS), Fagerstrom Test for Nicotine Dependence, International Physical Activity Questionnaire (IPAQ), and finally a Clinical Global Impression (CGI) scale.^[122, 123] All instruments and questionnaires will be administered via Partners RedCap. After each visit, the RA will also extract data from the patient's mental health clinic chart for information related to diagnostic changes, clinical developments, medication prescription, and any healthcare utilization.

The study nurse also will collect basic vital signs, e.g., EKG, weights, height (BMI, waist circumference), blood pressures and heart rate, and collect blood samples for laboratory tests, e.g., lipid panels, HbA1cs. As part of the baseline safety evaluation, we will collect additional laboratory test values, e.g., liver function tests. The study nurse

will receive laboratory values and provide appropriate follow up, which includes reporting any critical values to patient and care providers, referring for further treatment as indicated and documenting exclusion based on criteria listed in the protocol. The supervising physician of record for APRNs will be [name].

Obtaining Study Drugs: Study nurse practitioners will prescribe study medication for subjects as follows: simvastatin 20 mg once per day, and/or losartan 25mg once per day or atorvastatin 10mg once per day and/or valsartan 40 mg once per day. The grant will pay for study medications at no cost to participants. The McLean Hospital Research pharmacy will procure the study medication for all study sites and dispense prescriptions in 3 month supplies. The study staff will pick up prescriptions from the pharmacy and provide to the subject during the study visit. Since the medications will be provided the same day, investigators will not store medications in any way, other than to transport the mediations to the various study sites. Study staff will follow the same procedures for procuring and dispensing medications at all external sites. That is, study staff will procure medications from The McLean Hospital Research pharmacy the morning of external site visits and transport the medications to dispense at each site.

Additional Data Sources: There are other noteworthy data sources for this trial: 1) clinic records; 2) electronic health records for two clinics; 3) APCD. RAs will systematically review the visit schedules and local medical records from each clinic for each subject. Additionally, McLean is scheduled to roll out its electronic health record (Epic Systems) during the course of this study, which we have extensive experience using in other settings. These data sources will provide complementary data sources for cross-validation (e.g., pharmacy fills, see quality checks below) as well as longitudinal information on psychiatric visit adherence, primary care visit frequency, and major unfavorable clinical events, e.g., ED visits and hospitalizations for psychiatric or cardiovascular events.

The study staff will request that participants agree to have All Payers Claim Database (APCD) queried by study staff such that they may access all insurance claims made on behalf of the participant. The APCD is an excellent source of ancillary information to reconcile all patient report and medical record information. Participants will not be required to agree to have the APCD accessed in order to participate. There is a detailed data management plan that details how all data will be kept and how participant information with remain private. For secure data transmissions, we use a secure FTP, which is available through Partners Research Computing (RC). We then keep the data on our dedicated servers managed by RC, which are behind the Partners firewall. We limit data access such that only the programmer/analysts working on the project can access the data; the data remain on the servers at all time; and at no time, do any of the data leave the servers (e.g., no data on laptops, desktops, or other devices).

Blood Pressure Checks: Participants prescribed the ARB who exhibit symptoms of hypotension (e.g., syncope, dizziness) and/or have an SBP measurement of <100 mmHg at the follow-up visit will additionally be evaluated for orthostatic hypotension and

tachycardia. These participants will be asked to come back within one week for an additional blood pressure check and study PIs will be notified.

Subjects who exhibit a combination of any 2 of the 3 criteria (self-reported/observed symptoms, SBP <100 mmHg, or abnormal orthostatic measures) or all 3 criteria will be discontinued from the ARB for at least one week before coming back in for the additional safety follow-up. Study nurses will assess whether the signs/symptoms are still present, or have been alleviated after discontinuing the study drug. Study PIs will be contacted to make the decision to continue/discontinue the study drug.

If a participant exhibits only one of the three criteria at a routine follow-up visit (i.e. just self-report symptoms), we will not discontinue the ARB before the safety follow-up. If the subject continues to meet one of the three criteria at the safety follow-up, subjects will be asked to stop the ARB for at least one week, then come back in for reassessment. Depending on the nature of the symptoms, vitals, and blood pressure levels at this safety follow-up, study nurses will decide whether these symptoms are related to the ARB versus dehydration, other drug use, or other unrelated factors. Study PIs will be contacted and ultimately make the decision to either continue or discontinue the ARB. If the subject self-reports the above symptoms at the visit and they appear to be unrelated to any other physical signs at the safety visit, then study PIs/physicians will consider continuing the study drug and reassessing in a week versus stopping for one week and reassessing.

Once study PIs have come to a decision about continuing/discontinuing the ARB, all subjects will be asked to come back for an additional safety assessment one week after the decision to confirm that they are safe to continue the course of action recommended by our team.

Training/Skills Assessments: We have systematic RA and APRN research training programs in place:

Training: Dr. [name]'s division has an extensive RA training program directed by [name], which has sessions on participant recruitment, informed consent, chart review and discussion of symptom scales. [name] first conducts live patient interviews watched by RAs, and then the RAs conduct interviews observed by [name]. In all cases, trainees complete symptom scale forms; we have excellent interrater reliability for symptom scales (0.8-0.9). At the end of training [name] certifies RAs as competent to carry out these assessments. RAs also will receive similar training to perform their chart reviews. The APRNs will be certified by the Hospital as able to carry out safety checks, vital signs, and blood draws, as well as prescribe medications in the state of Massachusetts as part their job duties. The APRNs will join the RA training described above for the participant recruitment and informed consent portion. Whenever possible we will use standardized processes and forms, e.g., standardized study laboratory order forms.

